# **1 PREFACE**

This Statistical Analysis Plan (SAP) describes the planned analyses and reporting for the PrEggNut randomised controlled trial. The following documents were reviewed in preparation of this SAP:

- PrEggNut case report form (CRF) (20th March 2019);
- PrEggNut NHMRC project grant application (APP1147576);
- PrEggNut trial protocol (version 2, 11th June 2019).

Any deviations from the planned analyses detailed in this SAP will be clearly documented with reasons in a post-analysis version of the SAP. Any post-hoc analyses which are not identified in this SAP but are completed to support planned study analyses will also be clearly identified.

# **2 INTRODUCTION**

## 2.1 Background and rationale

Australia has the highest reported prevalence of food allergy in children in the world. Recent randomised controlled trials have shown that regularly including traditionally allergenic foods, such as egg and peanut, with solid foods from mid-late infancy reduces the risk of developing egg and peanut allergies in some infants. Australian studies, led by Chief Investigators [name], [name], [name], [name] and [name], have made a key contribution to clinical practice internationally in this field. Our findings also demonstrate that a significant proportion of infants have allergic reactions, including anaphylaxis, on first introduction of egg in solid foods as early as 4 months of age. We have recently shown that food-allergen (egg) specific immune responses can be established prior to infants eating any egg-allergen in solid foods. Furthermore, these responses were not altered by early introduction of egg in the infant diet. In other words, it is too late for many infants who are already allergic by the time these foods are introduced around 4-6 months of age.

Food allergens are first encountered before birth and can be detected in amniotic fluid, and in the immediate postnatal period in breastmilk. Intriguingly, the fetal immune system has been indicated to be particularly tolerogenic during this developmental period. Immune tolerance appears to be the default response to allergen encounter. Hence, early allergen exposure is a logical strategy for food allergy prevention. Accordingly, we have recently shown that higher maternal intakes of egg during early lactation can beneficially modify infant egg-specific immune responses. However, it is not known whether these changes are associated with a reduced likelihood of developing egg allergy in

Version 1.0

Statistical Analysis Plan

Page 5

infants. Hence this randomised controlled trial will investigate higher regular egg and peanut maternal dietary intakes during pregnancy and lactation as a strategy for infant food allergy prevention.

### 2.2 Objectives

To determine whether the incidence of food allergies in infancy can be reduced by a maternal diet rich in eggs and peanuts during pregnancy and lactation.

# **3 STUDY METHODS**

### 3.1 Trial design

Multi-centre, parallel, two-arm (1:1 allocation), researcher blinded (outcome data assessors, statistical analyst and investigators), randomised trial. Women with a singleton pregnancy who are planning to breastfeed for at least 4 months will be randomised to follow either a high (at least 6 eggs and 60 peanuts per week) or standard (no more than 3 eggs and 30 peanuts per week) egg and peanut intake diet from 22 weeks gestation until 4 months postnatal infant age. The primary outcome is food challenge proven IgE-mediated egg and/or peanut allergy in the infants at 12 months of age.

### 3.2 Randomisation

Pregnant women are assigned to a high egg and peanut diet (treatment group) or standard egg and peanut diet (control group) using a secure web-based randomisation service. The randomisation service allocates group assignments according to a computer-generated randomisation schedule, produced by an independent statistician using ralloc.ado version 3.7.6 in Stata version 15.1. Randomisation was stratified by city (Adelaide, Melbourne, Perth, Sydney) and by first or subsequent born child to the mother using randomly permuted blocks of varying sizes.

### 3.3 Sample size

To detect a reduction in egg and/or peanut allergy from 16% in the control group to 11.2% in the treatment group (absolute reduction 4.8%, relative reduction 30%) with 85% power and two-sided alpha of 0.049 at the final analysis, 961 women per group were required (with a continuity correction applied). Conservatively assuming 10% loss to follow-up, this led to a sample size estimate of 1068 women per group, or 2136 women total. Further details on the assumptions involved in the sample size calculations are provided in the PrEggNut trial protocol (Version 2, Section 5.7).

Statistical Analysis Plan

Page 6

### 3.4 Framework

All comparisons will be undertaken assuming a standard superiority hypothesis testing framework.

## **3.5** Statistical interim analyses and stopping guidance

An independent statistician will conduct a single interim analysis of the primary outcome once 961 infants (50% of the planned sample size, accounting for loss to follow-up) have primary outcome data available. The analysis will be performed according to the statistical methods described in Section 6. An independent Data Monitoring Committee will review the results of this analysis and employ O'Brien-Fleming stopping criteria (1) to maintain the overall alpha for the primary outcome across interim and final analyses at 0.05. A two-sided p-value of less than 0.0031 at the interim analysis (symmetric stopping boundary of  $Z = \pm 2.96259$ ), indicating a large difference between treatment groups, will be taken to provide statistical evidence in support of early stopping. A p-value of 0.0490 ( $Z = \pm 1.96857$ ) will be used to indicate statistical significance at the final analysis.

## 3.6 Timing of final analysis and unblinding

The database will be locked for analysis once data collection and cleaning are complete and the final version of this SAP has been approved. Following the database lock, blinded treatment codes will be made available to the trial statistician and analysis of the listed outcomes will be performed blinded to treatment group. Results of these analyses will be made available to the Trial Steering Committee members, with the blinding broken following a review of results.

### **3.7 Timing of outcome assessments**

The 12-month clinical outcome assessment should occur when infants are between 12 and 15 months of age. Outcome data collected outside this window will still be included in the main intention to treat analyses but excluded from a per-protocol analysis of the primary outcome (see Section 4.3).

# **4 STATISTICAL PRINCIPLES**

### 4.1 Confidence intervals and p values

For each outcome variable, a 95% confidence interval will be reported to express uncertainty about the estimated treatment effect. The statistical significance of the estimated treatment effect will be assessed at the 0.05 level using a two-sided comparative test, unless otherwise specified.

#### PrEggNut Study Statistical Analysis Plan

#### Page 7

In describing the effectiveness of the intervention, multiple hypothesis tests will be performed due to multiple secondary outcomes, subgroup analyses and sensitivity analyses for the primary outcome. No multiplicity adjustment will be made for the number of secondary analyses, as these are of less importance than the overall intention to treat (ITT) analysis of the primary outcome. In the absence of a formal procedure for controlling the type-I error rate, less emphasis will be placed on the results of secondary analyses.

## 4.2 Adherence and protocol deviations

Adherence to the intervention involves (a) following the recommended intake of egg and peanuts to 4 months postnatal age, and (b) continuing breastfeeding to 4 months postnatal age. Women will be considered to have adhered to diet recommendations if they reported meeting recommendations in the last week (at least 6 eggs and 60 peanuts for the treatment group, no more than 3 eggs and 30 peanuts for the control group) across at least 75% of their scheduled pre-natal and post-natal assessments. Depending on timing of birth, pre-natal assessments are scheduled at 26, 30, 34 and 38 weeks gestation, while post-natal assessments are scheduled at 1, 2, 3 and 4 months after delivery. Women with missing data on egg and peanut intake at a scheduled appointment will be considered to have adhered to the breastfeeding recommendations if they continue any breastfeeding, including use of expressed breast milk, until at least 4 months of age. Women with missing data on breastfeeding duration will be considered to have not met breastfeeding recommendations.

For each randomised group, frequencies and percentages will be presented for:

- Overall adherence (following dietary consumption and breastfeeding recommendations);
- Adherence to breastfeeding recommendations;
- Adherence to both egg and peanut dietary consumption recommendations;
- Adherence to egg consumption recommendations;
- Adherence to peanut consumption recommendations.

The participants included in the ITT analysis dataset (see Section 4.3) will be used as the denominator in the calculation of percentages. The number of eggs and peanuts consumed in the last week at each scheduled assessment for each randomised group will also be described using medians and interquartile ranges.

Version 1.0

Statistical Analysis Plan

Page 8

Frequencies and percentages (of the ITT analysis dataset) will also be presented separately by randomised group for the following protocol deviations:

- Ineligible participant randomised;
- Randomised in the wrong stratum;
- Given the wrong dietary recommendations according to randomisation;
- 12-month clinical outcome assessment not occurring between 12 and 15 months of age;
- Withdrawal from study;
- Loss to follow-up.

## 4.3 Analysis populations

For the primary outcome and secondary clinical outcomes (detailed in Sections 6.1 and 6.2), the planned analyses will be performed using an ITT approach. Excluding infant deaths occurring prior to outcome measurement (see Section 6.4.6 for more detail), the ITT population will include all randomised women-infant pairs, analysed as randomised, irrespective of eligibility or compliance with the protocol. For the primary outcome only, a sensitivity analysis will also be performed using a per-protocol approach. The per-protocol population will consist of all women-infant pairs that:

- Followed dietary consumption and breastfeeding recommendations (as described in Section 4.2);
- Did not report a protocol deviation (as described in Section 4.2);
- Provided data on the primary outcome at 12 months.

For exploratory laboratory outcomes (Section 6.3) collected in Perth and Sydney, the analysis population will consist of all women or infants that provided a blood sample at the relevant time point, analysed according to their randomised group.

Statistical Analysis Plan

Page 9

# **5 TRIAL POPULATION**

# 5.1 Screening data, eligibility, recruitment and withdrawal/follow-up

The following CONSORT flow diagram will be completed to document numbers screened and randomised and the flow of participants through the trial.

28/07/2021

Statistical Analysis Plan

Page 10

The number of screened women and exclusions from the trial (not meeting the protocol-defined inclusion criteria, declined to participate, withdrew consent and loss to follow-up) will also be reported separately for each city.

# 5.2 Baseline characteristics

A descriptive comparison of the randomised groups will be conducted on the baseline characteristics presented in the following table.

Baseline characteristic	Categories
City	Adelaide
	Melbourne
	Perth
	Sydney
Maternal age in years	-
Maternal ethnicity	Caucasian
	Aboriginal/Torres Strait Islander
	Maori/Pacific Islander
	African
	Middle Eastern
	Mediterranean
	East Asian
	South/South East Asian
	Other
Maternal school education - completion of secondary	Yes/No
school	
Maternal further education	No further study
	Certificate/diploma
	Degree
	Higher degree
Maternal smoking	Yes/No
Other smoking in the household	Yes/No
Pet dog(s)	Yes/No
Pet cat(s)	Yes/No

Version 1.0

PrEggNut Study Statistical Analysis Plan	Page 11
Pet chicken(s)	Yes/No
Parity	First born child
	Subsequent born child
Gestation at randomisation in weeks	-
Pre-pregnancy weight in kg	-
Current weight in kg	-
Maternal BMI in kg/m 	-
Maternal history of allergic disease	Yes/No
Paternal history of allergic disease	Yes/No
Sibling history of allergic disease	Yes
	No
	Not applicable
Maternal history of food allergy	Yes/No
Paternal history of food allergy	Yes/No
Sibling history of food allergy	Yes
	No
	Not applicable
Maternal peanut intake per week	-
Total household peanut intake per week	-
Maternal egg intake per week	-
Total household egg intake per week	-
Maternal egg specific-IgG4 levels	-
(Perth and Sydney women only)	
Maternal peanut specific-IgG4 levels	-
(Perth and Sydney women only)	
Infant sex	Female
	Male

Means and standard deviations, or medians and interquartile ranges will be reported for continuous variables. Frequencies and percentages will be reported for categorical variables. The clinical importance of any observed imbalances will be noted.

Version 1.0

#### Statistical Analysis Plan

Page 12

### **5.3** Post-randomisation characteristics

A descriptive comparison of the randomised groups will be conducted on the post randomisation characteristics presented in the following table:

Post-randomisation characteristic	Categories
Infant birth weight in kg	-
Infant gestational age at birth in weeks	-
Preterm birth < 37 weeks	Yes/No
Early preterm birth < 34 weeks	Yes/No
Infant birth mode of delivery	Vaginal
	Caesarean section
Ever breastfed	Yes/No
Breastfeeding during the whole intervention period until infant is 4 months	Yes/No
of age	
Breastfeeding up to 8 months of age	Yes/No
Breastfeeding up to 12 months of age	Yes/No
Breastfeeding duration in months*	-
Maternal mastitis during the intervention period	Yes/No
Maternal weight change during intervention period in kg	-
Infant given any infant formula during intervention period	Yes/No
Age at introduction to infant formula in months in infants given formula	-
Age at introduction to solid foods in months*	-
Age of introduction to egg in months*	-
Age of introduction to peanut in months*	-
Infant weight at 4 months of age in kg	-

\* Time to event variable

Means and standard deviations, or medians and interquartile ranges will be reported for continuous and time to event variables. Frequencies and percentages will be reported for categorical variables.

Version 1.0

Statistical Analysis Plan

Page 13

Differences between study groups will be tested using t-tests for continuous variables, Fisher exact tests for categorical variables and log-rank tests for time to event variables.

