### 6.4.2 Covariate adjustment

Given recommendations to adjust for variables used to stratify the randomisation when estimating treatment effects (4), analyses will be adjusted for city (Adelaide, Melbourne, Perth, Sydney) and

Version 1.0

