#### PrEggNut Study Statistical Analysis Plan

#### Page 16

birth order (first or subsequent born child to the mother). Adjustment will also be made for infant sex and maternal history of allergic disease (defined as a medical diagnosis of asthma, eczema, hayfever or food allergy), both considered important prognostic variables for infant allergic disease outcomes (5, 6). All adjustment variables will be treated as fixed effects in the analysis models. For each outcome, both unadjusted and adjusted analyses will be performed, with the adjusted analyses used to draw final conclusions about the effect of treatment.

If adjusted models fail to converge for any of the outcomes, adjustment variables will be removed sequentially (infant sex, then maternal history of allergic disease, then city, then birth order) until convergence is achieved. Adjusted analyses will not be considered for binary outcomes analysed using a Fisher exact test (see Section 6.4.1).

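### Section 5.3 tests post-randomisation characteristics without the stratification factors, so where city or birth order predicts a characteristic the tests are mildly conservative (a minor, nearly free improvement)

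*SAP*

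**What the plan says.** Section 3.2: "Randomisation was stratified by city (Adelaide, Melbourne, Perth, Sydney) and by first or subsequent born child to the mother". Four cities by two birth-order levels gives eight strata. Within each stratum the allocation was made "using randomly permuted blocks of varying sizes".

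Section 5.3 opens by calling itself descriptive: "A descriptive comparison of the randomised groups will be conducted on the post randomisation characteristics". After the table it adds hypothesis tests: group differences are "tested using t-tests for continuous variables, Fisher exact tests for categorical variables and log-rank tests for time to event variables". It names no stratification, covariate, effect estimate or interval. The table has 18 rows:

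- Five continuous: birth weight, gestational age at birth, maternal weight change, age at formula introduction among infants given formula, and infant weight at 4 months.
- Nine binary.
- Four marked as time to event: breastfeeding duration, and ages at introduction of solids, egg and peanut.

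Section 6.4.2 states the adjustment principle: "Given recommendations to adjust for variables used to stratify the randomisation when estimating treatment effects (4), analyses will be adjusted for city" and birth order, together with infant sex and maternal history of allergic disease. Its scope is worded by outcome: "For each outcome, both unadjusted and adjusted analyses will be performed, with the adjusted analyses used to draw final conclusions". It also makes an exception: "Adjusted analyses will not be considered for binary outcomes analysed using a Fisher exact test". Section 6.4.1 reserves the Fisher exact test for outcomes with fewer than 5 events in either group.

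**The concern.** Blocking within strata makes the two groups nearly equal in city and birth order. Between-stratum variation is thereby removed from the treatment difference, but a test that ignores the strata still counts it in the standard error. The test is then conservative for any characteristic that the strata predict. Birth weight, mode of delivery, breastfeeding duration and age at first egg or peanut could plausibly vary by birth order or city.

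The rows are not idle ones. They are measured after the intervention starts, so a difference could be an effect of the diet. Birth weight, preterm birth and breastfeeding are not in the harms list of Section 6.5, so Section 5.3 is the only place where the SAP tests them. Age at introduction of egg and peanut bears on how the primary result is read, since Section 2.1 says that feeding these foods to infants reduces allergy in some of them. A conservative test leans towards finding no difference.

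**Working it through.** **1. The plan's own figure.** Section 5.3 gives no number. The only related figure is the primary-outcome sample size (Section 3.3), which sets the trial size used below. With p1 = 0.16, p2 = 0.112, two-sided alpha 0.049 (z = 1.9686) and power 85% (z = 1.0364):

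- Uncorrected n = [1.9686 × √(2 × 0.136 × 0.864) + 1.0364 × √(0.1344 + 0.0995)]² / 0.048² = 919.5, so 920.
- With continuity correction: (919.5/4) × [1 + √(1 + 4/(919.5 × 0.048))]² = 960.7, so 961.
- With 10% loss: 961/0.9 = 1067.8, so 1068 per group and 2136 in total.

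All three stated figures (961, 1068, 2136) reproduce.

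**2. Continuous rows, by formula.** Let R² be the share of variance explained by city and birth order alone. The SAP gives no value, so a range is assumed. The unadjusted standard error is too large by 1/√(1 − R²). Hence:

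- true size = 2 × [1 − Φ(1.96/√(1 − R²))]
- unadjusted power where the adjusted test has 80% = Φ(1.960 + 0.842 − 1.96/√(1 − R²))

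| Assumed R² | True size at nominal 5% | Unadjusted power (adjusted = 80%) |
|---|---|---|
| 0 | 5.0% | 80.0% |
| 0.01 | 4.9% | 79.7% |
| 0.02 | 4.8% | 79.4% |
| 0.05 | 4.4% | 78.5% |
| 0.10 | 3.9% | 76.9% |
| 0.20 | 2.8% | 72.9% |

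Example, R² = 0.10: 1.96/√0.90 = 2.066. Size = 2 × [1 − Φ(2.066)] = 0.039. Power = Φ(2.802 − 2.066) = Φ(0.736) = 0.769.

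**3. All three test types, by simulation.** N = 2136, eight strata of equal expected size, blocks of 4, 6 or 8 (assumed; the SAP does not give block sizes). There were 15,000 null data sets per scenario and 3,000 under an alternative (mean difference 0.1213 SD, log odds ratio 0.27, log hazard ratio 0.13).

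- Modest strata effects: R² about 0.03 for the continuous variable; hazard ratio e^0.5 = 1.65 for birth order and e^0.3 = 1.35 between extreme cities.
- Strong strata effects: R² about 0.12; hazard ratios e^1.0 = 2.7 and e^0.9 = 2.5.

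| Test: plain vs stratified or adjusted | Size, modest | Power, modest | Size, strong | Power, strong |
|---|---|---|---|---|
| t vs linear model | 4.6 vs 4.9% | 78.3 vs 79.2% | 3.7 vs 4.9% | 76.4 vs 80.1% |
| Fisher vs Mantel-Haenszel | 4.5 vs 5.1% | 82.0 vs 82.9% | 3.9 vs 4.9% | 78.1 vs 80.9% |
| Log-rank vs stratified log-rank | 4.3 vs 4.8% | 75.5 vs 78.4% | 2.5 vs 4.6% | 63.5 vs 77.8% |

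Monte Carlo standard error is about 0.2 points for size and under 1 point for power.

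**4. Log-rank under other assumptions.** With 1922 pairs (2 × 961), treatment hazard ratio 1.14 for power, censoring at 12 months and 3,000 trials per setting:

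- Strata hazard ratios 1.5 (birth order) and 1.3 (across cities): size 4.6%; power 74% vs 76% stratified.
- Strata hazard ratios 2.0 and 1.5: size 3.7% vs 4.9%; power 71% vs 78%.

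The log-rank loss over both sets is therefore 2 to 3 points with modest strata effects (76 − 74; 78.4 − 75.5) and 7 to 14 with strong ones (78 − 71; 77.8 − 63.5).

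**The case against.** The best reply is that the SAP is internally consistent. Section 6.4.2 sits within 6.4, whose methods are for the outcomes of 6.1 to 6.3, and its rule is worded by outcome. Section 5.3 belongs to the trial-population chapter, lists characteristics and calls itself descriptive. Harms in Section 6.5 are also compared by unadjusted Fisher tests. No decision rule hangs on the Section 5.3 p-values, type I error stays at or below 5%, and most of the power losses are small. All of this stands. A reader might infer that the SAP contradicts itself by dropping an adjustment it requires; it does not require one here.

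Three further inferences are tempting, and none is supported:

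- That every Section 5.3 test is conservative. This holds only where city or birth order predicts the characteristic.
- That variance explained by infant sex also makes the tests conservative. Sex was not balanced by design, so omitting it costs precision but leaves the size of the t-test nominal. It does not belong in the R² above.
- That testing maternal weight change without the starting weight (listed in Section 5.2 as "Current weight in kg") is an error. A t-test on change is unbiased in a randomised comparison. Adjustment could gain precision, by an amount the SAP gives no means to calculate.

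Two parts of the reply do not carry. The descriptive label does not settle the matter: Section 5.2 carries the same label and has no tests, whereas Section 5.3 adds them. Nor does the Fisher exception reach this far: Section 6.4.1 uses Fisher only for sparse outcomes, while Section 5.3 applies it to every categorical row, including ones likely to be common, such as mode of delivery or formula use.

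**Conclusion.** The point holds as a minor improvement to precision. It is not an inconsistency in the SAP and not a threat to validity. For t and Fisher tests the expected loss is small: 0 to about 3 power points for R² up to 0.10, and just under 4 for the t-test in the strong scenario (R² about 0.12). The four log-rank rows are the most exposed. Their loss becomes material only with strong strata effects, and the 14-point figure needs hazard ratios of about 2.5 or more for both factors.

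The R² values, strata effects, treatment effects, block sizes and stratum sizes are all assumptions. The direction of the effect follows from the design; its size cannot be fixed from the SAP. Primary and secondary conclusions do not change, because those analyses already follow Section 6.4.2.

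**What to change.** Replace the testing sentence of Section 5.3 with the following:

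- **Time-to-event rows (four):** log-rank test stratified by city and birth order.
- **Continuous rows:** linear regression adjusted for city and birth order, reporting the adjusted difference and its 95% interval.
- **Binary rows:** log binomial regression adjusted for city and birth order, with the Poisson fallback of Section 6.4.1, reporting the relative risk and its 95% interval. Use the Fisher exact test where either group has fewer than 5 events, as in Section 6.4.1; early preterm birth may be such a row.

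Adjusting any row for infant sex, or maternal weight change for weight at randomisation, is an optional gain in precision and should be described as such.

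The cost is a few lines of SAP text and code. City and birth order are known for every woman from randomisation, and the unadjusted summaries stay in the table. If the sponsor prefers to keep the simple tests, Section 5.3 should at least say that they are unadjusted and that a non-significant result is not evidence of no difference.
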